Phase of trial	Phase II, proof-of-concept trial
Investigational medicinal product, Dose and Mode of Application	Trade Name: Nicotinell 14mg/24-Stunden-Pflaster Substance: Nicotine Manufacturer: GlaxoSmithKline Dose: 14mg/24h Mode of application: transdermal patch Duration of treatment: 7 days
Comparative Drug, Dose and Mode of Application	Placebo patch Patchinga® Freestyle Libre 3 Manufacturer: Shanghai Ruiquan Medical Equipment Co., Ltd Dose: not applicable Mode of Application: patch Duration of Treatment: 7 days
Auxiliary medicinal product, Dose and Mode of Application	Not applicable
Indication	Male and female patients with benign and malignant lesions of the periampullary region (e.g. pancreatic carcinoma, distal bile duct carcinoma, duodenal carcinoma, ampullary carcinoma, cystic lesions, chronic pancreatitis) requiring pancreatoduodenectomy
Trial Design	Multi-center, prospective, randomized, double blind, placebo controlled

Objectives	Endpoints
Primary	
To assess the effect of transcutaneous administration of nicotine as compared to placebo on the development and severity of delayed gastric emptying (DGE) following pancreatoduodenectomy	Grade of delayed gastric emptying (none, grades A-C representing increasing severity) according to the consensus definition of the International Study Group of Pancreatic Surgery
Secondary	
To evaluate the safety, efficacy and tolerability of transcutaneous nicotine administration as compared to placebo in patients requiring pancreatoduodenectomy	
Assessment of tolerability:
 
 • postoperative pancreatic fistula • postpancreatectomy hemorrhage • intraabdominal fluid collections • surgical site infections • re-intervention rate • re-operation rate • Clavien-Dindo classification • MTL30 score • quality-of-life questionnaires (QLQ-C30 and PAN26) • mortality • cardiovascular events ((non-fatal) myocardial infarction, (non-fatal) stroke, revascularization during admission) 
Assessment of efficacy on DGE-development:
 
 • requirement of naso-gastric tube (NGT) in the first 21 days after surgery • inability to tolerate solid oral food in the first 21 days after surgery • vomiting/gastric distension in the first 21 days after surgery • use of prokinetics in the first 21 days after surgery 
Additionally, the following parameters are used for grading (according to the International Study Group of Pancreatic Surgery)
 
 • comorbidities • specific treatment • nutritional support • diagnostic evaluation • interventional treatment • prolongation of hospital stay • delay of potential adjuvant therapy

Confidential

EU trial No: 2023-503349-71-00/ TransNiDeG

Clinical Trial Protocol version 2.0 28-JUN-2023

Attachment 001 to SOP MW-009.001

Version 001

Effective Date: 18-Mai-2022

	
Assessment of safety: Adverse Events and Serious Adverse Events

Subject Number	
Four-hundred (400) subjects will be pre-assessed for eligibility, from whom 300 are expected to sign the informed consent and be eligible for surgery. A total number of 240 subjects will be randomized for IMP treatment (120 per treatment arm).

Inclusion Criteria	
Subjects will only be included in the clinical trial if they meet all of the following criteria:
 
General inclusion criteria:
 
 1. Subjects aged ≥ 18 years 2. given written informed consent to participate in the trial 
Indication-specific inclusion criteria:
 
 3. planned for pancreatoduodenectomy 4. smokers must be willing to stop smoking for the duration of the IMP application (i.e. from Day 1 to Day 7)
Exclusion Criteria	
Subjects will not be included in the clinical trial if any of the following criteria applies:
 
General Exclusion Criteria:
 
 1. Subject without legal capacity who is unable to understand the nature, scope, significance and consequences of this clinical trial 2. Simultaneous participation in a clinical trial taking an investigational medicinal product, up to 30 days prior to last IMP intake in that clinical trial. 
Exclusion criteria regarding special restrictions for females:
 
 3. Current or planned pregnancy or nursing women 4. Females of childbearing potential, who are not using and not willing to use medically reliable methods of contraception for the entire study duration (such as oral, injectable, or implantable contraceptives, or intrauterine contraceptive devices) unless they are surgically sterilized / hysterectomized or there are any other criteria considered sufficiently reliable by the investigator in individual cases 
Indication specific exclusion criteria:
 
 5. distant organ metastases (which can be diagnosed after screening, e.g. during surgery; then no resection is performed according to guidelines) 6. former gastrectomy 7. liver fibrosis/cirrhosis

Confidential

EU trial No: 2023-503349-71-00/ TransNiDeG

Attachment 001 to SOP MW-009.001

Version 001

Page 12 of 69

Clinical Trial Protocol version 2.0 28-JUN-2023

Effective Date: 18-Mai-2022

	
 8. Known history of hypersensitivity to nicotine or a component of the investigational drug 9. Systemic skin diseases (e.g. Lupus erythematoses) 10. Immediately after heart attack 11. Severe cardiac arrhythmia 12. Stroke that occurred shortly before 13. Concomitant medication with inhibitors or strong inducers of CYP2A6 (e.g. Trancylpromine, Desipramin, Ketoconazole, Valproic acid, Pheno-barbital, Pilocarpine, Clotrimazole, Methoxsalen, Rifampicin)
Trial Procedures	
Screening-Visit (Day -28 to Day -1)
 
Visit 1 (Day 1, Surgery)
 
Visit 1.2 – 1.7 (Post-operative Day 2 to Day 7)
 
Visit 2 (Post-operative Day 14)
 
Visit 3 (Post-operative Day 21 or discharge – whatever comes first)
 
Visit 4 (Post-operative Day 30, follow Up)

Trial Specific Measurements	
 • Application of IMP-/Placebo-patch • Assessment of primary and secondary endpoints
Investigational trial sites	
This is a multi-center trial with about six (6) investigational trial sites in Germany.

Statistical Rationale	
The primary objective of the trial is to estimate the rates of DGE grades within the defined populations during a 21 days period after surgery after 7 days treatment either with nicotine or with placebo patch.
 
These rates will be given together with their respective confidence intervals by treatment group. A comparison of the treatment groups will be performed by means of a proportional odds model (accounting for the stratification factors center and smoking status). The main outcome of this analysis will be an estimate of the odds ratio according to the explorative character of the trial.
 
Additional sensitivity analyses will be performed to assess the robustness of the results: a dichotomized version of the DGE score will be investigated by means of a logistic regression model.
 
In both models, the influence of additional covariates like sex, age, or other comorbidities will be investigated (for the purpose of the planning of later phase trials).
 
Two analysis populations will be defined: intent-to-treat (ITT) and per-protocol (PP). The former includes all randomized patients whereas patients with relevant protocol deviations will be excluded from the latter. The main analysis will be performed within the ITT population.

Confidential

EU trial No: 2023-503349-71-00/ TransNiDeG

Clinical Trial Protocol version 2.0 28-JUN-2023

Attachment 001 to SOP MW-009.001

Version 001

Effective Date: 18-Mai-2022

	
Safety parameters and secondary endpoints will be summarized by means of descriptive statistics or by absolute and relative frequencies according to the type of the variables by treatment.

Time Schedule
	
Per Subject:
 
 • 28 days for Screening + 30 days treatment phase = maximum 58 days in total 
Trial duration:
 
 • Recruiting Period: 24 months • Planned Start Date (FPFV/ FPI): August 2023 • Planned End Date (LPLV/ LPO): August 2025

2 Schedule

	Screening Visit	Treatment Phase		Follow up Phase		End of Trial
Time points (accepted deviation)	Day -28 to Day -1	Day 1 (Surgery)	Day 2 to Day 7	Day 14 (+/- 1 Day)	Day 21 (+/-1 Day) or Discharge	Day 30 (+/- 2 Days)
Visit No.	0	1	1.2 to 1.7	2	3	4
Informed Consent	√					
Demographics	√					
Medical History (including request for pregnancy in females of childbearing potential)	√					
Concomitant medication	√	√	√	√	√	√
In-/Exclusion Criteria	√	(√) ⁴				
Application of IMP		√ (during or immediately after surgery)	√			
Grading DGE ¹			√	√	√	
AEs and SAEs ²		√	√	√	√	√
Checks for secondary Endpoints ³		√	√	√	√	√
Histopathology					√	
Days of postoperative stay (i.e. from post-operative Day 1 until Discharge)					√	
MTL30						√

Confidential

EU trial No: 2023-503349-71-00/ TransNiDeG

Attachment 001 to SOP MW-009.001

Version 001

Page 15 of 69

Clinical Trial Protocol version 2.0 of 28-JUN-2023

Effective Date: 18-Mai-2022

	Screening Visit	Treatment Phase		Follow up Phase		End of Trial
Time points (accepted deviation)	Day -28 to Day -1	Day 1 (Surgery)	Day 2 to Day 7	Day 14 (+/- 1 Day)	Day 21 (+/-1 Day) or Discharge	Day 30 (+/- 2 Days)
Visit No.	0	1	1.2 to 1.7	2	3	4
QLQ-C30						√
PAN26						√

¹ according to the definition of the International Study Group of Pancreatic Surgery. NGT requirement + solid food intake on every visit day indicated, all other parameters only on Visit 1.3, 1.7, 2 and 3.

² especially: surgical site infections, cardiovascular events, mortality

³ Visit 1 only Lymphadenectomy, re-intervention, re-operation, nausea, cardiovascular events. Visit 1.2, 1.3, 1.5-1.7 no assessment. Visit 1.4, 2, 3, 4 only pancreatic fistula, postoperative hemorrhage, intra-abdominal fluid collections, re-laparotomy

⁴ Exclusion Criterion No. 5 can only be answered during surgery

3 Abbreviations

AR	Adverse (Drug) Reaction
AE	Adverse Event
AMG	Arzneimittelgesetz
CA	Competent Authority
CI	Coordinating Investigator
CRA	Clinical Research Associate
CRF	Case Report Form
CRO	Contract Research Organization
CTR	Clinical Trial Regulation
DGE	Delayed Gastric Emptying
EC	Ethics Committee
FPFV	First Patient First Visit
FPI	First Patient In
GCP	Good Clinical Practice
GDPR	General Data Protection Regulation
ICH	International Conference on Harmonization
IMP	Investigational Medicinal Product
ISF	Trial site File
LPLV	Last Patient Last Visit
LPO	Last Patient Out
NGT	Naso-gastric tube
PD	Pancreatoduodenectomy
PI	Principal Investigator
SAR	Serious Adverse Reaction
SAE	Serious Adverse Event
SDP	Sponsor Delegated Person
SUSAR	Suspected Unexpected Serious Adverse Reaction
SZB	Study Center Bonn (Studienzentrum Bonn)
UAR	Unexpected Adverse Reaction

4 Trial Administration structure

Coordinating Investigator and Sponsor Delegated Person	[name] Department of Surgery University Hospital Bonn [name] [contact] Email: [contact]
Sponsor	Medical Faculty of the University of Bonn, represented by the Dean [name]
Coordinating institution	Clinical Study Core Unit, Study Center Bonn (SZB) Institute for clinical chemistry and clinical pharmacology University Hospital Bonn [name]
Participating trial site(s)	6 German sites are planned

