11.1.7 Checks for Endpoints

The following checks will be performed on the dates indicated in the study schedule:

- Occurrence of pancreatic fistula
- Occurrence of postoperative hemorrhage
- intraabdominal fluid collections
- re-intervention rate
- re-operation rate
- nausea
- occurrence of cardiovascular events
- re-laparotomy

Confidential

EU trial No: 2023-503349-71-00/ TransNiDeG

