12.5.1 Serious Adverse Events exempted from expedited reporting

According to the ICH Guideline E19² in certain situations selective safety reporting may be appropriate. This applies for example if the IMP has received a marketing authorization from a regulatory authority, the safety profile is well-known, the clinical pharmacology has been described and understood, post-authorization data is sufficiently available.

In this clinical trial the test-IMP has a marketing authorization for more than 30 years in Germany and a very well-know safety profile from a large number of post-authorization data [54]. The aim of this trial is to provide evidence of efficacy of nicotine treatment in patients suffering from DGE after PD.

Surgical resection is a pre-planned procedure and not considered as trial treatment. Therefore, complications from surgical resection (PD) from the date of surgery until the end of follow-up are not considered AEs/SAEs unless the complications are considered to be related to treatment with the IMP. Surgical complications will be documented in the eCRF and the patient file.

Furthermore, events that are probably related to the underlying disease are not considered as AE/SAE as long as the severity of the event is to be expected and not aggravated.

² ICH Guideline E19 on a selective approach to safety data collection in specific late-stage pre-approval or post-approval clinical trials (16-Mar-2023)

The underlying disease is a condition prior to inclusion in the clinical trial. Events that are probably related to the underlying disease are not considered as AE/SAE as long as the event and the severity of the event are to be expected and not aggravated.

The following events are most likely to occur after surgical resection or are most likely related to the underlying disease:

- Postoperative pancreatic fistula
- Relaparotomy
- Postoperative haemorrhage
- Insufficiency of the biliodigestive anastomosis
- Insufficiency of the GE (Gastroenterostomy)
- (Superficial) wound infections
- Intra-abdominal abscess
- Pleural effusion
- Pneumonia

In recent studies, nicotine application was extremely safe in terms of anastomotic healing and surgical site infections [59,60]

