14.2.2 Secondary Target Variables

The secondary objective is to evaluate the safety and tolerability of transcutaneous nicotine administration as compared to placebo in patients requiring pancreatoduodenectomy.

Secondary Endpoints

Assessment of tolerability:

- postoperative pancreatic fistula
- postpancreatectomy hemorrhage
- intraabdominal fluid collections
- surgical site infections
- re-intervention rate
- re-operation rate
- Clavien-Dindo classification
- MTL30 score
- quality-of-life questionnaires (QLQ-C30 and PAN26)
- mortality
- cardiovascular events ((non-fatal) myocardial infarction, (non-fatal) stroke, revascularization during admission)

Assessment of efficacy on DGE-development:

- requirement of naso-gastric tube (NGT) in the first 21 days after surgery
- inability to tolerate solid oral food in the first 21 days after surgery
- vomiting/gastric distension in the first 21 days after surgery
- use of prokinetics in the first 21 days after surgery

Additionally, the following parameters are used for grading (according to the International Study Group of Pancreatic Surgery)

- comorbidities
- specific treatment
- nutritional support
- diagnostic evaluation
- interventional treatment

Confidential

EU trial No: 2023-503349-71-00/ TransNiDeG

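### Schedule footnote 3 checks re-interventions only on the day of surgery, Clavien-Dindo has no assessment visit, and surgical site infection is routed in two contradictory ways

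*Protocol*

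**What the plan says.** Section 14.2.2 lists re-intervention rate, re-operation rate, surgical site infections, "Clavien-Dindo classification" and "cardiovascular events ((non-fatal) myocardial infarction, (non-fatal) stroke, revascularization during admission") among the secondary endpoints for tolerability.

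Section 11.1.7 names the endpoint checks but sets no dates of its own: "The following checks will be performed on the dates indicated in the study schedule". The schedule in Section 2 ticks the row for secondary endpoint checks in every column from surgery on. Footnote 3 then restricts it in three steps:

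- For the day of surgery it gives one set of items: "Visit 1 only Lymphadenectomy, re-intervention, re-operation, nausea, cardiovascular events".
- Five of the six visits on Days 2 to 7 are then left without any check.
- The four remaining visits get a closed list: "Visit 1.4, 2, 3, 4 only pancreatic fistula, postoperative hemorrhage, intra-abdominal fluid collections, re-laparotomy".

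Footnote 2, attached to the AE/SAE row, says "especially: surgical site infections, cardiovascular events, mortality". That row is ticked from Day 1 to Day 30.

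Section 12.5.1 says that "complications from surgical resection (PD) from the date of surgery until the end of follow-up are not considered AEs/SAEs" unless they are judged related to the IMP, and its list of typical events includes wound infections. It adds that surgical complications go into the eCRF and the patient file, without naming a visit, a time window or a grading. Section 12.4 collects AEs from first dosing until discharge.

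**The concern.** Re-intervention and re-operation after pancreatoduodenectomy are postoperative events. A check on the day of the index operation cannot give their rate. If sites follow footnote 3 as written, the re-intervention rate rests on whatever other forms happen to record.

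Clavien-Dindo grade is a declared endpoint that no visit asks for. For surgical site infection, a site that follows footnote 2 and a site that follows Section 12.5.1 would record the same infection differently. With about six sites, that invites uneven recording between sites.

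Tolerability is part of the stated secondary objective. A statistical analysis plan can define how an endpoint is derived, but it cannot supply events, dates or grades that were not collected.

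**Working it through.** No formula applies. The check sets the schedule, its footnotes and Sections 11.1.6, 11.1.7, 12.2.1, 12.4 and 12.5.1 side by side and counts scheduled assessments.

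**Visits from surgery on.** Visit 1, Visits 1.2 to 1.7 (six visits), and Visits 2, 3 and 4: 1 + 6 + 3 = 10.

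**Reading of footnote 3.** The first sentence can mean that these items are checked at Visit 1 and nowhere else, or that Visit 1 checks these items and no others. Both readings lead to the same place. The second sentence removes five visits (1.2, 1.3, 1.5, 1.6, 1.7), and the third confines the remaining four to a closed list that omits re-intervention and re-operation.

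**Coverage by item.**

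| Item | Secondary endpoint? | Dedicated check, of 10 visits | Other scheduled route |
|---|---|---|---|
| Re-intervention | Yes | 1 (Visit 1) | Abscess drain and relaparotomy within DGE grading, 4 visits (1.3, 1.7, 2, 3) |
| Re-operation | Yes | 1 (Visit 1) | Re-laparotomy, 4 visits (1.4, 2, 3, 4) |
| Clavien-Dindo | Yes | 0 | None |
| Surgical site infection | Yes | 0 | AE/SAE row, 10 visits, contradicted by 12.5.1 |
| Cardiovascular events | Yes | 1 (Visit 1) | AE/SAE row, 10 visits |
| Nausea | No | 1 (Visit 1) | Reportable as an AE |

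**Re-intervention.** The interventional item in Table 1 of Section 11.1.6 serves DGE grading and names abscess drain and relaparotomy. It is last assessed at Visit 3, which is Day 21 or discharge, whichever comes first. From there to the Day 30 visit is nominally at least 30 − 21 = 9 days, and longer after an earlier discharge. In that stretch a re-intervention other than re-laparotomy has no scheduled check.

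**Re-operation.** The re-laparotomy check covers most of it. A re-operation that a site does not class as a re-laparotomy has no dedicated check after Day 1.

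**Clavien-Dindo.** The AE form cannot stand in for it. AE intensity in Section 12.2.1 is mild, moderate or severe, and Section 12.5.1 keeps surgical complications out of the AE data unless they are IMP-related.

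**Surgical site infection.** Footnote 2 makes it an AE item. Section 12.5.1 makes surgical complications non-AEs unless IMP-related and lists wound infections among the typical events. The eCRF recording it asks for instead has no visit attached, and Section 11.1.7 has no infection check.

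**AE window.** Section 12.4 ends AE collection at discharge, while the schedule ticks AEs and SAEs at Day 30. A patient discharged before Day 30 falls under two different rules.

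**The case against.** The strongest reply is that other routes run alongside footnote 3, and much of it stands.

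- Footnote 2 names cardiovascular events and surgical site infections in a row ticked at every visit from surgery on.
- Myocardial infarction and stroke are not on the Section 12.5.1 list, and collection to discharge fits an endpoint whose wording refers to the admission.
- Nausea is not a listed secondary endpoint. It is a known nicotine effect and is reportable as an AE. Vomiting and prokinetic use are also assessed in DGE grading.
- Re-laparotomy is checked at four later visits.
- Section 12.5.1 requires surgical complications in the eCRF whatever their cause.
- The eCRF manual and data management plan are separate documents, so the absence of eCRF fields cannot be asserted.

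A reader might therefore go too far in several ways:

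- That these endpoints will be close to empty. The parallel routes speak against it.
- That surgical site infection has no check at all, or counts only when the patch is blamed. It has a nominal AE route and an unscheduled eCRF route. The fault is that the protocol does not say which applies, or when.
- That re-intervention, re-operation, nausea and cardiovascular events are all observed on 1 day of 30. That describes dedicated checks only.
- That the DSMB could not see harm. Section 13 has it review safety data in both arms, leaves details to a charter and lets the Coordinating Investigator submit any trial data.

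What the reply does not remove is the missing re-intervention check after Day 1, the missing assessment point for Clavien-Dindo, and the conflict between footnote 2 and Section 12.5.1.

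**Conclusion.** The point holds for three secondary endpoints. Re-intervention rate has a dedicated check at 1 of 10 visits, on the day of surgery, and partial coverage through DGE grading that ends at Visit 3. Clavien-Dindo is assessed at 0 of 10 visits. Surgical site infection has contradictory routing and no dedicated check. Two smaller inconsistencies go with it: re-operation is followed later only as re-laparotomy, and the AE window differs between Section 12.4 and the schedule. For cardiovascular events and nausea, the Day 1 check is a wording fault with little consequence, because AE collection continues.

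The primary endpoint is not affected, and Section 14.2.5 plans only descriptive summaries of secondary endpoints. The risk is an incomplete re-intervention rate, an unsupported Clavien-Dindo endpoint and uneven infection counts. The number of events that would be missed cannot be derived from the protocol.

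The conclusion assumes that sites follow the schedule as written, and that the bracket in the Table 1 interventional item is a list. If the bracket gives examples, coverage up to Visit 3 is wider, but re-interventions after Visit 3 are still unchecked apart from re-laparotomy.

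**What to change.** 1. In footnote 3, keep lymphadenectomy at Visit 1. Move re-intervention and re-operation to the existing check visits 1.4, 2, 3 and 4, asking each time for any event since the last check, with its date.
2. Add surgical site infection and Clavien-Dindo grade to Section 11.1.7 and to the same visits. State that they are recorded for every patient, whatever the AE classification or the causality judgement.
3. Reconcile footnotes 2 and 3 with Sections 11.1.7, 12.4 and 12.5.1, so that there is one stated route for surgical site infection and one end to AE collection. Align the nausea and cardiovascular checks at the same time.

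The visits already exist. The cost is an edit to the footnote and to those sections, plus a few more eCRF fields per visit. Dates and grades that were not collected may not be recoverable, so the change should come before enrolment or as early in it as possible.

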The most frequent complication following pancreatoduodenectomy (PD) is delayed gastric emptying (DGE) with a reported incidence of 19%-57% [1]. A wide range of causative mechanisms has been proposed for DGE: the absence of hormonal stimulation due to the resection of the duodenum, ischemia of the stomach and duodenum following resection, denervation of the stomach and duodenum, post-operative pylorospasm, DGE secondary to other intraabdominal complications, pancreatic fibrosis, cholangitis, pancreatitis, alteration of the endocrinologic milieu or torsion/angulation of the reconstructed alimentary tract [2]. In fact, most studies concentrating on DGE accused technical aspects of the reconstruction to cause DGE, but none was able to ameliorate DGE. Neither ante- or retrocolic reconstruction route [3], pylorus resection and –preservation [4], nor single versus double loop reconstruction [5] does influence the frequency of DGE following PD. Often, DGE is self-limiting [2] and does not increase periprocedural mortality [6,7], but DGE is known to significantly increase hospital stay [8]. Recently DGE was described for the first time to negatively affect cancer specific survival [9]. So, strategies are needed for the treatment of delayed gastric emptying to increase the utilization of adjuvant chemotherapy with the goal of improved overall survival.

The aim of this clinical trial is to assess the effect of transcutaneous administered nicotine on the development and severity of delayed gastric emptying (DGE) following pancreatoduodenectomy (PD) as compared to placebo.

